7.3.2. Total Number of Days of Exposure

The total number of exposure days (EDs) along with the duration of dosing to rFVIII Fc and total number of injections per subject will be summarized. The summary will use the Safety Analysis Set; these data will be summarized.

In this summary, for any subject, the total number of EDs, duration of dosing to rFVIII Fc, and total number of injections will be calculated from the start date and time of the starting treatment regimen to the end date and time of the last treatment regimen in study 8HA01EXT. The start and end of treatment regimens are defined in Section 5.3.1. An ED is a 24-hour period in which one or more rFVIII Fc injections are given. The 24-hour window starts from the first rFVIII Fc injection on the study and then for subsequent injections, it starts from an injection taken after/outside of a previously identified ED.

The total number of EDs on rFVIII Fc for each subject will be summarized categorically (<50, 50-<100, 100-<150, 150-<200, 200-<250, etc.) and with descriptive statistics. The total number of injections per subject will be summarized using descriptive statistics.

Any interruptions to dosing will be ignored for the purposes of calculating the interval. The number and percentage of subjects whose duration of dosing was at least 13 weeks, at least 26 weeks, at least 39 weeks, at least 52 weeks, and at least 78 weeks will be tabulated based on the integer part of the calculated week.

Duration of rFVIII Fc dosing (weeks) will also be summarized using descriptive statistics. Weeks will be represented in the descriptive statistics as if these were data collected with 1 decimal place.

This table will also be presented by subgroup based upon contemporaneous entry compliance of \leq 80%, as described in Section 6.5.5.3.

7.3.3. Total Annualized rFVIII Fc Consumption

The secondary endpoint of total annualized rFVIII Fc consumption per subject for the prevention and treatment of bleeding episodes will be summarized for the FAS. See Section 6.5.4 for details on the annualized rFVIII Fc consumption derivation.

7.3.4. Physician's Global Assessment of the Subject's Response to His rFVIII Fc Regimen

Investigators will record assessments of each subject's response to his rFVIII Fc regimen at each scheduled visit using the following 4-point scale:

- 1=Excellent: bleeding episodes responded to \leq the usual number of injections or \leq the usual dose of rFVIII Fc, or the rate of breakthrough bleeding during prophylaxis was \leq that usually observed.
- 2=Effective: most bleeding episodes responded to the same number of injections and dose, but some required more injections or higher doses, or there was a minor increase in the rate of breakthrough.
- 3=Partially Effective: bleeding episodes most often required more injections and/or higher doses than expected, or adequate breakthrough bleeding prevention during prophylaxis required more frequent injections and/or higher doses.
- 4=Ineffective: routine failure to control hemostasis or hemostatic control requires additional agents.

Investigators should consider the following, if available, when making the assessment:

- Frequency of rFVIII Fc injections
- Response to rFVIII Fc injection
- Information reported in the eDiary by the subject

The physician's global assessment of the subject's response will be summarized by visit for overall treatment regimen for the FAS. The number and percentage of subjects in each response category will be tabulated. Percentages will be based on the number of subjects for whom an assessment was provided at the respective visit. This table will also include a cumulative tabulation across all scheduled study visits; subjects can be included in this tabulation up to all visits, once for each visit. Percentages for this collection of responses throughout the study will be based on the total number of assessments across all visits. In addition, these assessments will be provided in a data listing.

7.3.5. Subject's Assessment of Response to rFVIII Fc Injections for Bleeding

Each subject or subject's caregiver will provide an assessment of response to each administration of rFVIII Fc for each bleeding episode using the 4-point scale of excellent, good, moderate, and none (see Appendix A for further details; 'none' means that there was no improvement, not that the subject did not provide a response). Response categories of excellent and good will be presented combined as well as individually. The number and percentage of injections in each response category will be tabulated based on all injections. Two summaries will be provided. In the first summary percentages will be based on the total number of injections administered for bleeding episodes for which a response was provided. In the second summary percentages will be based on the total number of bleeding episodes whether or not a response was provided. As a supplemental analysis, similar summaries will be provided based on just the first injection administered after each bleeding episode using both approaches to determine the percentages.

- The subject's assessment of response will be summarized for the FAS.

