7.1.4.2. Procedure to Treat the Bleeding Episode

The dose of rFVIII Fc to treat the bleeding episode will be based on the subject’s clinical condition, known PK information from the previous study or FVIII trough/peak (recovery) measurements in this study, type and severity of the bleeding event (see [Appendix A](#) for guidance on dosing), and input from the Sponsor, if necessary.

Subjects and subjects’ caregivers should be instructed to treat at the first sign of a bleeding episode with a single dose of rFVIII Fc. Most bleeding episodes should resolve with a single dose of rFVIII Fc. If a subject has one spontaneous bleed and the Investigator is concerned the trough level is too low, the Investigator should contact the Sponsor to discuss next steps for this subject.

- **If the bleeding episode stops with a single IV dose of rFVIII Fc**, the subject should return to his previous dosing regimen and will be treated with his next dose of rFVIII Fc as previously scheduled, even if this results in consecutive daily doses.
- **If the bleeding episode does not stop within 24 hours with the single IV dose of rFVIII Fc**, the subject or the subject’s caregiver should consult with the Investigator for an optimal rFVIII Fc dose and dosing interval, and should administer a second dose (first follow-up dose) no less than 24 hours after the initial dose. Administration of the second dose of rFVIII Fc as follow-up treatment will be determined by the Investigator based on the subject’s clinical condition. Please refer to [Appendix A](#) for rFVIII Fc dosing guidance. Once the bleeding event stops, the subject will return to his previous dosing

CONFIDENTIAL

The information contained herein may not be used, disclosed, or published without the written consent of
Biogen Idec MA Inc.

regimen and will be treated with his next dose of rFVIII Fc as previously scheduled, even if this results in consecutive daily doses.

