Bleeding at a different location will occur when the general bleeding location is different (e.g., in a joint for the original bleeding episode and subsequently in a muscle) or in a sub-location not initially present if in the same location category (e.g., right elbow for the original bleeding episode and subsequently in the right and left elbows). Conversely, a bleeding episode that originally occurs in the right elbow and left knee and is reported as a new bleed within 72 hours as being only in the right elbow will be considered to be in the same location and hence not counted as a new bleeding episode.

A bleeding episode that occurs in multiple locations will be counted as a single event when determining the overall annualized number of bleeding episodes. However, in summaries by bleeding location, the bleeding episode will be counted in each location for which it is reported with the exception that bleeding that occurs in more than one sub-location of the same location category (e.g., 2 or more different joints) will be counted as just one for that location category.

Only bleeding episodes that were treated with at least one dose of FVIII (whether rFVIII-Fc or a non-study drug) will be included in the analysis of endpoints evaluating bleeding. That is, bleeding episodes that were not treated at all will not be included. Bleeding episodes that were treated with non-study medication will be included in the determination of the annualized bleeding rate. The handling of bleeding episodes treated with non-study FVIII for other endpoints is discussed in Sections 7.4.1.

Bleeding episodes of an unknown type will be included in the determination of the annualized bleeding rate and in summaries based on bleeding episodes but, unless specified otherwise, will not be included in summary tables where endpoints are summarized by type of bleed.

The per-subject annualized number of bleeding episodes, hereafter referred to as the annualized bleeding rate (ABR), will be calculated for each subject using the following formula:

$$\text{ABR} = \frac{\text{Number of bleeding episodes during the efficacy period}}{\text{Total number of days during the efficacy period}} \times 365.25$$

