7.4. Additional Assessments

7.4.1. Number of Injections and Dose of rFVIII Fc to Resolve a Bleeding Episode

The number of injections, average dose per injection (IU/kg), and total dose (IU/kg) required to resolve a bleeding episode will be determined on both a per-bleeding episode and per-subject basis. See Section 7.1.1 for details on the definition of a bleeding episode. A bleeding episode is considered resolved when treatment for the bleeding is no longer needed.

Per bleeding episode: The total number of injections will include the initial injection for a spontaneous bleed (SB), a traumatic bleed (TB), or a bleed of unknown type plus all injections identified as follow-up (FU) treatment for that bleed. For each bleed, the average dose per injection will be calculated as the average of all doses (IU/kg) administered among the SB/TB/Unknown and FU injections administered to treat that bleed; the total dose will be the sum of these doses. The number of injections required for the resolution of a bleeding episode will be summarized across all bleeding episodes in study 8HA01EXT both categorically (1, 2, 3, >3; 1, >1; and ≤ 2 , >2) and with descriptive statistics. The average dose per injection and total dose required for resolution of a bleeding episode will be summarized using descriptive statistics.

Per subject: The number of injections, average dose per injection, and total dose required to resolve each bleeding episode, as determined for the per-bleeding episode summaries, will be averaged across all bleeding episodes in study 8HA01EXT for each subject. The average number of injections required for resolution of a bleeding episode will be summarized both categorically (1 to <2, 2 to <3, and ≥ 3) and with descriptive statistics. The averages for the per-subject average dose per injection and total dose required for resolution of a bleeding episode will be summarized using descriptive statistics.

Bleeding episodes that were treated with both study and non-study medication will be included in the determination of the number of injections required to resolve the bleeding episode but not in either the average dose per injection or total dose required.

For the above analysis, data from the FAS will be summarized.

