Inj Reason	Reason of injection changed (other than routine prophylaxis or other to surgical prophylaxis if a confirmed minor/major surgery or procedure is capture in the eCRF during the defined surgical period or date of procedure; or from new bleed to follow up)	Y
Inj Reason Surgery	Injection reason from routine prophylaxis or other to surgical prophylaxis	N
BLD LOC	Change in Bleed Location	Y
BLD TYP	Change in Bleed Type	Y
BLD SYM	Change in Bleed Symptoms	Y
DTOB	Date and/or time of bleed corrected	Y
Activity	Change in Physical Activity question	Y
TRT SD	Amendment to Treat with Study Drug item: “Did you inject with rFVIIIFc (Study Drug)?”	Y
TRT BLD	Amendment to Treat Bleed item: “How did the bleed respond to injection on ...”	Y
Abandon	Query request was raised but then cancelled by site	N
In-clinic administration	In-clinic administration entered in EPD and corrected in reference to source records	N
NBTFU	Injection to treat the bleed is < 72 h of the previous injection to treat the existing bleed New bleed deleted, follow up inj to existing bleed added (per protocol definition)	N
Tx Arm/Reg	Change in treatment arm or regimen	N
ADMIN	Changes made by site to data fields that the site would have entered originally and/or are administrative. E.g. study name or data entered into an incorrect field and corrected, data entered that is not required, expiry date of IMP extended, data field changes that are duplicated due to multiple site staff involved in the query process or similar, correction of injection reason related to treatment arm, e.g. routine prophylaxis to weekly dose for subjects on a weekly regimen	N

In certain circumstances, where subjects could not enter records directly into the EPD for any reason, records were requested to be created manually by the site according to a pre-defined documented process which included SDV by CRA. However, it was subsequently identified that confirmation of SDV could not be provided. Records were re-SDVed at site to determine whether source was available, or whether contemporaneous documentation of confirmation with the subject was available. *(Not discussed further in this SAP).*

For the impact assessment, all data record changes requiring subject confirmation will be set back to the original values. Although changes classified as SVC/L60 did not require subject confirmation (as agreed with MHRA in 2014), these changes will no longer be made directly into

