the data, but will be applied via a programmatic data convention (described in Section 5.4). Manually created data without complete SDV of the record versus a paper diary will be considered unsupported by SDV at site, and will be removed for the purpose of the impact assessment. SDTM and ADAM datasets will be re-created and certain statistical analyses re-run. Endpoints covered under the impact assessment include:

- exposure
- annualized number of bleeding episodes per subject (ABR)
- subjects assessment of response to treatment with rFVIII Fc for bleeding episodes
- number of injections and dose per injection of rFVIII Fc required to resolve a bleeding episode
- prophylactic dose and dosing interval

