9.2 Existing Outputs to be Re-run

The summary tables will be regenerated based on updated ADAM datasets are shown in Table 5.

Table 5: Summary Tables Rerun With the Updated Datasets

Outputs	Summary Table titles	Program file name
Disposition	Disposition	T-DISPOSITION.SAS
Exposure	Summary of exposure	T-EX-SUM.SAS.SAS
	Summary of prophylactic dose (IU/kg)	T-EX-PROPHY-DOSE.SAS
	Summary of prophylactic dose and interval	T-EX-PROPHY-DOSE-INT.SAS
ABR	Summary of annualized bleeding rate	T-ABR-SUM.SAS
Subject response to treatment of bleed	Summary of subject's assessment of response to rFVIII Fc injections for the treatment of bleeding episodes	T-SUBJ-ASSESS-RESP-BLD.SAS

Injections and dose required for resolution of a bleeding episode	Summary of number of injections required for resolution of a bleeding episode	T-INJ-RES-BLD.SAS
Injections and dose required for resolution of a bleeding episode	Summary of dose (IU/kg) of rFVIIIc for resolution of bleeds	T-DOSE-RES-BLD.SAS

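### SAP 7.3.5 divides injections by bleeding episodes in its second response summary, and SAP 7.3.2 never annualizes the exposure-days endpoint

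*SAP*

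**What the plan says.** **Response to treatment of bleeds.** SAP 7.3.5 has the subject or caregiver rate every administration and sets the unit of count: "The number and percentage of injections in each response category will be tabulated based on all injections". It then gives two denominators. The first is injections with a rating. For the other it states: "In the second summary percentages will be based on the total number of bleeding episodes whether or not a response was provided". A supplement repeats both approaches for the first injection of each bleed only.

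SAP 7.4.1 counts, for each bleed, the initial injection "plus all injections identified as follow-up (FU) treatment for that bleed", with categories up to more than three. Protocol 16.4.3.2 describes the same endpoint in another unit: the number and percentage of bleeding episodes with each response. The table is among those re-run in the impact assessment (SAP 9.2: "Summary of subject's assessment of response to rFVIII Fc injections for the treatment of bleeding episodes").

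**Exposure days.** Protocol 6.2.2 and SAP 2.2.2 both list exposure days (EDs) per subject per year as a secondary endpoint. SAP 7.3.2 defines an ED and summarizes total EDs, total injections and duration of dosing. SAP 6.5.1.1 only refers to 7.3.2, and Protocol 16.6.2 plans total EDs. The SAP's list of outputs names annualized consumption and annualized bleeding rate (ABR), but no annualized EDs. ABR (SAP 7.1.1) and consumption (SAP 6.5.4) each have a formula ending in × 365.25.

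**The concern.** In the second all-injections summary the numerator and denominator are in different units. That summary evidently exists to show the result when unrated treatment stays in the denominator, so it should be the more cautious of the pair. Divided by bleeds, it loses that property: every follow-up injection that is rated adds to the numerator and nothing to the denominator.

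For EDs, the SAP as written would leave a named secondary endpoint unreported. Total EDs mix dosing frequency with length of follow-up, so they can order subjects or regimens differently from the yearly rate. The SAP also fixes no time base for anyone who computes the rate later.

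**Working it through.** The plan states no figure to reproduce. The check compares units and then illustrates the size.

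**Response table.** Let m = rFVIIIFc injections per bleed, r = share of injections rated, g = share of rated injections that are excellent or good.

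- Rated-only summary: g.
- All injections as denominator: g × r, which can never exceed g.
- As written, per bleed: g × m × r. The ratio to the line above is m, and the categories sum to 100 × m × r %.
- The as-written figure exceeds the rated-only figure only if m × r > 1.

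None of m, r or g is in the documents, so all values below are assumptions. Protocol 7.1.4.2 expects that "Most bleeding episodes should resolve with a single dose of rFVIII Fc". If a share s of bleeds needs one injection and the rest exactly two, m = 2 − s, which is 1.05, 1.10 or 1.25 at s = 95%, 90% or 75%. With g = 75%, excellent/good (%) is:

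| Denominator | r = 0.70 | r = 0.85 | r = 1 |
|---|---|---|---|
| All injections (any m) | 52.5 | 63.8 | 75.0 |
| Bleeds, m = 1.05 | 55.1 | 66.9 | 78.8 |
| Bleeds, m = 1.10 | 57.8 | 70.1 | 82.5 |
| Bleeds, m = 1.25 | 65.6 | 79.7 | 93.8 |

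At r = 0.85, for example, 0.75 × 0.85 = 63.75%, and 63.75 × 1.10 = 70.1%. The categories then sum to 85 × m = 89.25%, 93.5% and 106.25% at the three values of m. The rated-only 75% is exceeded when r > 1/m, that is, above 0.952, 0.909 and 0.800.

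The rated-only summaries have matching units. In the first-injection summary over all bleeds the units nearly match. The exception is bleeds treated only with non-study product, which SAP 7.1.1 counts: "Only bleeding episodes that were treated with at least one dose of FVIII (whether rFVIII-Fc or a non-study drug) will be included". Those have no rFVIIIFc injection to rate.

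**Exposure days.** Assume regular dosing.

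- Weekly: 365.25 / 7 = 52.2 EDs per year. Over 4 years, the maximum in SAP 3.1, the total is 208.7.
- Twice weekly: 365.25 / 3.5 = 104.4 EDs per year. Over 1 year the total is 104.4.
- The weekly subject has 2.0 times the total at half the yearly rate.
- Twice weekly for 13, 26 and 52 weeks gives 26, 52 and 104 EDs, which fall in three different SAP 7.3.2 categories at one rate.

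The time base matters too. SAP 7.3.2 counts from the start of the starting regimen to the end of the last regimen. The efficacy period used for ABR and consumption (SAP 5.3.2) removes surgical periods and prophylaxis gaps of more than 28 days. For a twice-weekly subject over one year (assumed cases):

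- A 60-day gap gives 305.25 / 3.5 = 87.2 per year in the 7.3.2 window, 16.4% below the 104.4 found with the gap removed.
- Fourteen days of daily surgical dosing gives 351.25 / 3.5 + 14 = 114.4, 9.6% above 104.4.

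**The case against.** **The slip may be in the numerator.** Protocol 16.4.3.2 uses bleeding episodes, so the misplaced word in SAP 7.3.5 could be injections rather than episodes. This stands: the two documents need reconciling, and the SAP text alone does not settle which word was meant. It does not rescue the rule as written, which is in neither unit.

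**A near-coherent per-bleed table already exists.** The first-injection supplement over all bleeds is close to what the protocol describes. This also stands, and the fix uses it. The table shells, which are not in the documents, might specify the right denominator, but the SAP text should not depend on them.

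**The effect is modest if most bleeds need one injection.** At m = 1.05 to 1.10 and r = 0.85 the inflation is about 3 to 6 points, and the figure stays below the rated-only 75%. This is correct.

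**Dosing frequency is already reported.** Duration accompanies total EDs in SAP 7.3.2, a subject listing of exposure is planned, and SAP 6.5.3 gives the average prophylactic dosing interval. Separate summaries of EDs and duration do not give a distribution of per-subject rates. The dosing interval leaves out intervals interrupted by bleeds and does not exist for episodic treatment.

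**A stronger reading of the re-run.** In the impact assessment "all data record changes requiring subject confirmation will be set back to the original values", and manual records without full source verification are removed. A reader might infer that this percentage could then shift with no change in ratings. The documents do not support that. The as-written figure is rated excellent/good injections over bleeds, so with both fixed it cannot move. If m rose from 1.10 to 1.20 through unrated records alone, it would stay at 70.1%, while the injection-based figure would fall to 63.75 × 1.10 / 1.20 = 58.4%. Changes to the ratings are themselves among those reverted. What carries into the re-run is only the wrong denominator.

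**Conclusion.** Both defects hold on the text.

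The second all-injections summary in SAP 7.3.5 overstates every category by the factor m whenever m exceeds 1. The size rests on assumed m, r and g: at g = 75% and r = 0.85, 66.9% to 70.1% at m = 1.05 to 1.10 and 79.7% at m = 1.25, against 63.8%. A reader might infer that the table will show totals above 100%, or will look better than the rated-only table. Either happens only if m × r > 1, and the documents give no basis for saying that it will.

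The yearly exposure-day endpoint has no derivation and no output in either document. The subject-level data allow it to be computed, so this is a missing specification, not missing data.

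No formal test is planned, and sample size is not affected. The changes are still worth making, because each alters or supplies a reported secondary result.

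**What to change.** **SAP 7.3.5.** In the all-injections table, and in its SAP 9.2 re-run, make the second denominator all injections given for bleeding episodes, rated or not. State that the first-injection summary over all bleeding episodes is the per-episode result that answers Protocol 16.4.3.2.

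**SAP 7.3.2.** Add, per subject, annualized EDs = EDs / days × 365.25.

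- Take EDs and days from the window that 7.3.2 already defines. Use the SAP 5.3.1 regimen duration for by-regimen rows.
- Apply the full SAP 5.3.2 minimum: more than 0 days for episodic treatment and at least 2 prophylactic injections for prophylaxis. Without it, one ED in a two-day prophylaxis spell would annualize to 365.25 / 2 = 182.6.
- Footnote that this window, unlike the efficacy period behind ABR and consumption, keeps surgical periods and gaps of more than 28 days.

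**Cost.** The response table needs one phrase and one sentence. The exposure table needs one formula, one footnote and one added row. No new data are required. The second response percentage becomes less favourable, by the factor m. Annualized EDs will not share a time base with ABR and consumption, and short episodic spells can still give extreme rates, so the median should be read alongside the mean.
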